2.6 OTHER MODIFICATIONS MADE TO THE STATISTICAL ANALYSIS PLAN

This section summarizes other changes to the SAP during this amendment, based on interpretation of the Protocol.

Other SAP amendment changes

Description of change to SAP	Reason for revision
Kaplan-Meier (Time-to-event) analyses deleted from SAP Section 6.5.	The protocol specifies only that the times between successive bleeds be summarized descriptively.
Replace lab analysis using CTCAE by PCSA. Lab analysis by NCI CTCAE grade and shift tables are removed in Section 6.8.3 since PCSA analysis will be performed. Vital sign by PCSA is added in Section 6.8.4 .	To be aligned with Sanofi's standard analysis for Lab and vital sign.
Treatment period is defined to be the onset period plus the efficacy period.	The term "treatment period" is defined in Section 6.3 for consistency with other Fitusiran studies.
The 'treatment policy strategy' of analyzing the ABR is added to the primary analysis.	Added in Section 6.3.1 for consistency and comparison with other Fitusiran studies.
In the LTE14762) study we will consider untreated bleeds as well as treated bleeds in efficacy analyses.	Modifications made to Section 6.3 to the effect that additional analyses will be performed which will include all bleeds, both treated and untreated.
Concomitant medication was removed from safety variables in Section 3.2.4 .	Typo corrected.
'Patient' was replaced by 'participant' throughout the document except for description of study design.	Align with company standard.
Analysis sets are defined for participants receiving original dose and regimen and participants receiving revised dose and regimen separately. Covid unaffected sets and full analysis sets are described in Section 4 .	Treatment regimens are different before and after the dosing pause in 2020. Analysis sets are refined accordingly. Inclusion of covid unaffected sets to evaluate the impact of pandemic on the study. Inclusion of full analysis sets for efficacy analysis.

Description of change to SAP	Reason for revision
Description of intercurrent events is updated in Section 6.3..	Inclusion of 2020 voluntary dose pause. Update the definition of missing 2 consecutive dose for revised dose and regimen.
An additional baseline defined for safety analysis after the 2020 dosing pause.	Given the duration of voluntary dose pause in 2020, an additional baseline for selected safety endpoints is added to better evaluate the safety profile of revised dose and regimen.
Imputation rule for AE is updated in Section 5.8.	Align with Sanofi standard.
Inclusion of analysis window for revised dose and regimen.	Describe the analysis window for revised dose and regimen.
Specify analysis in general will be performed under original dose and regimen and under revised dose and regimen separately in Section 6. Describe planned analysis under revised dose and regimen.	To better evaluate the safety and long-term efficacy of revised dose and regimen.
Describe analysis for dosing interruption periods in Section 6.5.	To evaluate the AT recovery and bleeding during dosing pause in 2017 clinical hold and 2020 voluntary dose pause.
Describe algorithm of identifying cholecystitis and cholelithiasis in Section 6.8.2.	Align with other studies of fitusiran.
Describe analysis of liver function in Section 6.8.3	Additional analysis of liver function.
Description of subgroups to be analyzed in Section 6.11.	Inclusion of subgroups to be analyzed. Given the extended duration of treatment post TDR14767(ALN-AT3SC-001), the treatment type before parent study entry has limited impact on efficacy evaluation. Subgroup analysis of treatment type before enrollment into TDR14767(ALN-AT3SC-001) will be removed.

2.7 MODIFICATION MADE IN SAP TO THE STATISTICAL SECTION IN PROTOCOL

Description in SAP	Rationale	Description in Protocol
The analysis periods are defined in Section 6.3. The start of analysis periods is the date of fitusiran with at least 20mg since parent study entry.	Prior exposure on fitusiran in TDR14767(ALN-AT3SC-001) may impact the efficacy evaluation in LTE14762. The analysis will incorporate the parent study data and extension study data for a comprehensive assessment of efficacy on bleeding.	Annualized bleed rate estimate will be calculated as the number of bleed events occurring 4 weeks after the first dose of fitusiran in this study and until the End of Study visit.

3 OBJECTIVES AND ENDPOINTS

3.1 OBJECTIVES

3.1.1 Primary objective

To evaluate the long-term safety and tolerability of fitusiran in male patients with moderate or severe hemophilia A or B.

3.1.2 Secondary objectives

To investigate the long-term efficacy of fitusiran

To characterize the safety and efficacy of concomitantly administered factor VIII (FVIII), factor IX (FIX), or bypassing agents (BPA) and fitusiran for treatment of bleeding episodes

To assess changes in health-related quality of life (QoL) over time

To characterize antithrombin (AT) reduction and thrombin generation (TG) increase

To characterize the pharmacokinetics (PK) of fitusiran.

3.1.3 Exploratory objectives

To assess safety and hemostatic efficacy rating for operative procedures conducted in patients while on study.

3.2 ENDPOINTS

3.2.1 Efficacy endpoints

Annualized bleeding rate (ABR) during the efficacy period

Annualized spontaneous bleeding rate during the efficacy period

Annualized joint bleeding rate during the efficacy period

Time intervals between bleeding events

Annualized weight-adjusted consumption of FVIII, FIX and BPA

Quality of life (QoL) measured by EuroQol 5-dimension 5-level (EQ-5D-5L) score

QoL measured by Haem-A-QoL score.

3.2.2 Pharmacokinetic endpoints

Plasma PK parameters of ALN-AT3SC

Urine PK parameters of ALN-AT3SC.

3.2.3 Pharmacodynamic endpoints

AT activity level over time

TG over time.

3.2.4 Safety variables

Adverse events (AE)

Clinical laboratory parameters

Vital signs

12-lead ECGs

Physical examinations.

3.2.5 Antidrug antibody endpoints

Incidence and titer of antidrug antibodies to fitusiran.

4 PARTICIPANT POPULATION

The following populations/analysis sets may be evaluated and used for presentation of the data.

Safety analysis set 1: All participants who receive at least a partial dose of study drug during the LTE14762 study under the original dose and regimen (ie, before the 2020 voluntary dose pause). The analysis set will be the main analysis set for analysis under original dose and regimen except for efficacy analysis and pharmacodynamics analysis.

Safety analysis set 2: All participants who receive at least a partial dose of study drug during the LTE14762 study under the revised dose and regimen (ie, after the 2020 voluntary dose pause). The analysis set will be used in safety analysis under revised dose and regimen. The analysis set will be the main analysis set for analysis under revised dose and regimen except for efficacy analysis and pharmacodynamics analysis.

Full analysis set 1: All participants in safety analysis set 1. The analysis set will be used in efficacy analysis and pharmacodynamics analysis under original dose and regimen.

Full analysis set 2: All participants in safety analysis set 2. The analysis set will be used in efficacy analysis and pharmacodynamics analysis under revised dose and regimen.

Per protocol set 1: All participants in the safety analysis set 1 who have no major protocol violations under the original dose and regimen in the following categories

- Failure to meet key eligibility criteria, which will be identified prior to database lock
- Prophylactic use of factor treatment or BPA (except for prophylaxis of bleeding in patients who require procedures or surgeries)

The protocol violation will be manually reviewed and adjudicated prior to database lock.

Per protocol set 2: All participants in the safety analysis set 2 who have no major protocol violations under the revised dose and regimen in the following categories

- Failure to meet key eligibility criteria, which will be identified prior to database lock
- Prophylactic use of factor treatment or BPA(except for prophylaxis of bleeding in patients who require procedures or surgeries)

The protocol violation will be manually reviewed and adjudicated prior to database lock.

PK analysis set 1: All participants who receive at least one dose of study drug and have at least 1 blood sample collection post-dose to determine plasma concentrations of study drug during the LTE14762 study under the original dose and regimen (ie, before the 2020 voluntary dose pause).

PK analysis set 2: All participants who receive at least one dose of study drug and have at least 1 blood sample collection post-dose to determine plasma concentrations of study drug during the LTE14762 study under the revised dose and regimen (ie, after the 2020 voluntary dose pause).

PD analysis set 1: All participants who receive at least one partial dose of study drug and have at least 1 blood sample collection post-dose to determine plasma AT and TG levels during the LTE14762 study under the original dose and regimen (ie, before the 2020 voluntary dose pause).

PD analysis set 2: All participants who receive at least one partial dose of study drug and have at least 1 blood sample collection post dose to determine plasma AT and TG levels during the LTE14762 study under the revised dose and regimen (ie, after the 2020 voluntary dose pause).

Operative procedure analysis set 1: All participants who received at least one partial dose of study drug and underwent at least 1 operative procedure during the LTE14762 study under the original dose and regimen (ie, before the 2020 voluntary dose pause).

Operative procedure analysis set 2: All participants who received at least one partial dose of study drug and underwent at least 1 operative procedure during the LTE14762 study under the revised dose and regimen (ie, after the 2020 voluntary dose pause).

Covid-19 unaffected set 1: All participants who have no major or critical protocol deviations due to Covid-19 during the study period under the original dose and regimen (ie, before the 2020 voluntary dose pause).

Covid-19 unaffected set 2: All participants who have no major or critical protocol deviations due to Covid-19 during the study period under the revised dose and regimen (ie, after the 2020 voluntary dose pause).

The Safety Analysis Set 1 and Safety Analysis Set 2 will be the primary sets for safety assessments, and for analyses of the efficacy and durability of fitusiran treatment. The PK Analysis Set 1 and PK Analysis Set 2 will be used for PK analysis and the PD Analysis Set 1 and PD Analysis Set 2 will be used for PD analyses. The PP Analysis set 1 and PP Analysis set 2 will also be used to assess the long-term efficacy of fitusiran treatment. The Operative procedure analysis set 1 and Operative procedure analysis set 2 will be used to assess safety and hemostatic efficacy in participants undergoing operative procedures while on study.

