6.5.1.3 Antithrombin level criteria for a dose adjustment

With the introduction of the new dose and regimen with Protocol Amendment 07 following the global program dosing pause implemented by Sponsor in 2020, patients will receive fitusiran treatment according to the below antithrombin level scenarios and criteria. See the rationale for a new dosing justification in Section 1.5. Dose modification rules are detailed in the section below and displayed in Figure 1 and Figure 2.

A) Dose restart

- a) Restart at 50 mg Q2M
- Patients that reach AT activity levels ≥22% (per central laboratory),
- Patients previously exposed to fitusiran at a dose of 50 mg QM or 80 mg QM with more than one AT activity level <15% (per central laboratory) at any time during fitusiran treatment,
- Patients will resume dosing at a dose of 50 mg Q2M and follow the modified IMP regimen SoAs (Table 3).
- b) Restart at 50 mg QM or 80 mg QM (prior dose)
- Patients that reach AT activity levels ≥22% (per central laboratory),
- Patients previously exposed to fitusiran at a dose of 50 mg QM or 80 mg QM with no more than one AT activity level <15% (per central laboratory) at any time during fitusiran treatment (based on at least 3 months of prior AT measurements),
- Participant may have the option to remain on that dose and follow the SoAs in Table 1 and Table 2.

B) Dose escalation

- a) Dose escalation to 50 mg QM
- After a period of dosing at 50 mg Q2M,
- Based on 2 steady state AT values >35% at the 50 mg Q2M dosing regimen,

- At least 2 of the 3 AT samples taken pre-dose at PR Month 4, PR Month 5 and PR Month 6 must be >35% to meet the escalation rule,
- Patients who previously had more than 1 AT value <15% at the 50 mg QM dose are not eligible to re-escalate to this dose level,
- If escalation rules are met, patient will receive the 50 mg dose at PR Month 7 (this will be considered the PR Month 1 of 50 mg QM, ie, the second 50 mg QM dose).

Note: If any of the doses prior to PR Month 6 are missed, then the decision-making for escalation must be shifted accordingly.

- b) Dose escalation to 80 mg QM
- After a prior escalation to the 50 mg QM dosing regimen,
- Based on 2 steady state AT values >35% at the 50 mg QM dosing regimen,

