A change in the fitusiran dosing regimen(referred as ‘revised dose and regimen’ throughout this SAP) has been introduced as a risk mitigation measure for vascular thrombotic events in Protocol Amendment 07. As the risk of vascular thrombotic events is thought to be increased in the setting of low AT activity levels, a reduced dose of 50 mg administered SC once every 2 months has been selected to minimize the occurrence of AT activity levels below 10%. At a reduced dose of 50 mg every 2 months, if a patient has more than 1 AT level <15%, the patient will be required to permanently discontinue fitusiran. Patients previously exposed to fitusiran at a dose of 50 mg monthly or 80 mg monthly with no more than 1 AT activity level <15% at any time during fitusiran treatment (based on at least 3 months of prior AT measurements) may have the option to remain on either dose, respectively.

If a patient receiving fitusiran 50 mg once every 2 months has 2 steady state AT levels above 35%, the patient will be dose escalated to fitusiran 50 mg monthly. In very rare cases, if a patient still has 2 steady state AT levels above 35% at the 50 mg monthly dose, the patient will escalate to

the 80 mg monthly dose. Detailed dosing adjustment plan can be found in Protocol Amendment 09 section 6.5.1.3.

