precision as the units of measure. The other statistics will be reported with 1 greater decimal place. Any values that require transformation to standard units (metric or SI) will be converted with the appropriate corresponding precision.

To be consistent with the compound level wording, ‘revised dose and regimen’ will be shown as ‘recommended dose and regimen’ in the statistical output.

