- For participant who remain the original dose regimen after the dose pause, the analysis visit will be derived based on original visit schedule (ie, Month xx), which will be reported following the original visit scheme. The first dose date after the dose pause will be assigned as Day1. The subsequent visits can be assigned based on the first visit accordingly. For example, the first visit after dose re-start is reported as “Month 36”, then the next visit is reported as “Month 37”. The Month 36 visit should be assigned as “PR Day 1” and the Month 37 should be assigned as “PR Month 1”. For unscheduled visit, the analysis visit will be populated based on treatment day after dose re-start. The analysis visit window will be derived as the middle-point of the target day between the 2 consecutive scheduled visits for each of the assessment. The target day is calculated as 30 days of visit interval times corresponding scheduled months plus 1. The treatment day after the volunteer dose pause is defined in [Section 5.2](#).

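### Set 2, labelled the revised (printed as recommended) dose and regimen, pools unchanged monthly dosing with the reduced 50 mg Q2M regimen, and the ABR and safety sections state no split by post-pause dose

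*SAP*

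**What the plan says.** SAP 4 defines a second version of each analysis set. Safety analysis set 2 takes everyone who received at least a partial dose "under the revised dose and regimen (ie, after the 2020 voluntary dose pause"). The efficacy set follows directly: "Full analysis set 2: All participants in safety analysis set 2".

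SAP 2.1 introduces the revised dose and regimen as the Amendment 07 change and says that "a reduced dose of 50 mg administered SC once every 2 months has been selected to minimize the occurrence of AT activity levels below 10" percent. The same paragraph adds that patients with no more than one AT level below 15% on 50 or 80 mg monthly "may have the option to remain on either dose, respectively". Protocol 6.5.1.3 has the same restart option: "Participant may have the option to remain on that dose and follow the SoAs in Table 1 and Table 2".

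SAP 5.10 gives these people their own visit rule: "For participant who remain the original dose regimen after the dose pause, the analysis visit will be derived based on original visit schedule". Their visits are then mapped to PR Day 1, PR Month 1 and so on.

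SAP 5.2 sets the default table columns as hemophilia type, inhibitor type and overall, and says that revised will appear in the output as "recommended dose and regimen". It also has one general sentence saying that treatment after the pause is handled as each participant's treatment sequence. SAP 6.4 applies treatment sequence to the pharmacodynamic analysis. SAP 6.3.1.1 (ABR) and 6.8 (safety) do not mention it.

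Protocol 10.2 promises summary tables by starting dose level and by final dose level or frequency. Protocol 10.2.6 promises TEAE incidence by dose level and overall.

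**The concern.** Membership of Set 2 is a matter of calendar time, while its label names a regimen. A participant still on the dose he had before the pause is counted, and printed, under the same heading as one moved to 50 mg every 2 months.

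The stated purpose of the latest amendment is to collect enough data to assess efficacy and safety of the revised dose and regimen. Protocol 1.5 and 1.6 link thrombotic risk to low AT activity, and the regimen was changed for that reason. Bleeding and thrombosis are thus the outcomes for which a reader will want to know which dosing produced the result.

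Those who could stay on monthly dosing were selected on their AT history, so the two groups differ in more than dose. With at most 48 patients enrolled, a few participants can move an overall rate.

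**Working it through.** No sample size, power or stated effect is involved, so there is no plan figure to reproduce. The check sets the definitions side by side and then sizes the mixing.

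**1. Who is in Set 2.** SAP 4 has one criterion, dosing after the 2020 pause. Protocol 6.5.1.3 A(b) allows restart at the prior 50 or 80 mg monthly dose. Anyone taking that option meets the criterion.

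**2. What the SAP calls them.** SAP 4 equates revised with after the pause. SAP 5.10 has a rule beginning "For participant who remain the original dose regimen after the dose pause" and assigns these participants post-restart visits. The same people are revised in one section and original in the other. SAP 2.6 explains the separate sets by regimens differing before and after the pause, which is not so for a participant whose dose did not change.

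**3. What the tables separate.**

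| Output after the pause | Split by post-pause dose or sequence stated? |
|---|---|
| PD (SAP 6.4) | Yes, by treatment sequence |
| ABR (SAP 6.3.1.1) | No; by period and every 6 months |
| AE and AESI (SAP 6.8, 6.8.2) | No; before and after the pause, with by-indication columns |
| Default (SAP 5.2) | No; hemophilia type, inhibitor type, overall |
| Protocol 10.2 and 10.2.6 | Yes; starting and final dose level or frequency, TEAEs by dose level |

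SAP 2.7, which lists SAP changes to the protocol's statistical section, records only the start of the efficacy analysis period.

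**4. How different the exposures are.** Nominal monthly dose:
- 50 mg every 2 months: 50 / 2 = 25 mg
- 50 mg monthly: 50 / 25 = 2.0 times as much
- 80 mg monthly: 80 / 25 = 3.2 times as much

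With the month lengths in SAP 5.10 (28 days for post-restart visits, 30 days for unchanged monthly dosing), the daily doses are 50/56 = 0.893, 50/30 = 1.667 and 80/30 = 2.667 mg. The ratios become 1.87 and 2.99.

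**5. Mean nominal monthly dose in the pooled set.** Let f be the share on unchanged dosing. The documents do not give it, so the values of f are assumptions. Everyone else is taken to be on 50 mg every 2 months. The mean is 25(1 − f) + 50f if all unchanged participants are on 50 mg monthly, and 25(1 − f) + 80f if all are on 80 mg.

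| f | Mean, mg per month | Relative to 25 mg |
|---|---|---|
| 10% | 27.5 to 30.5 | 1.10 to 1.22 |
| 25% | 31.25 to 38.75 | 1.25 to 1.55 |
| 50% | 37.5 to 52.5 | 1.50 to 2.10 |

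**6. What pooling could do to mean ABR.** Pooled mean = (1 − f)a + fb, with a the ABR on 50 mg every 2 months and b the ABR on unchanged monthly dosing. All values of a and b are assumed.

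| a, b | f = 10% | f = 25% | f = 50% |
|---|---|---|---|
| 4, 1 | 3.70 | 3.25 | 2.50 |
| 4, 2 | 3.80 | 3.50 | 3.00 |
| 2, 2 | 2.00 | 2.00 | 2.00 |
| 1, 4 | 1.30 | 1.75 | 2.50 |

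Pooling can lower the figure, leave it alone or raise it. The documents do not say which.

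**The case against.** The best defence is that revised dose and regimen means the whole Amendment 07 scheme. SAP 2.1 states the option to stay in the paragraph that introduces the term, and Protocol 6.5.1.3 lists it among the AT-based scenarios. Participants who stay are also subject to the new rules: the AT threshold for restart, the AT history test, and the requirement to change regimen after more than one AT level below 15%. The amendment rationale wants at least 18 months of data after introduction whether or not a patient changed regimen. This stands. A reader might infer that the Set 2 results fail to describe the revised regimen at all. The documents do not support that, because on the scheme-wide meaning the pooled results are what was intended.

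A reader might also infer that the SAP ignores treatment sequence outside PD. That goes too far. The general sentence in SAP 5.2 closes a paragraph on dose classification for efficacy and safety, and a figure that follows it is not shown in the text available and may list the sequences. What remains is that the ABR and safety sections do not invoke it, whereas the PD section does.

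Finally, a reader might infer a definite percentage bias in ABR. Nothing in the documents gives the share on unchanged dosing or the ABR in either group. The direction cannot be derived either, since the groups were formed on AT response to earlier dosing.

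**Conclusion.** The point holds as a matter of labelling and presentation. Set 2 contains everyone dosed after the pause. Its pooled results are valid for the AT-guided scheme as a whole but cannot be attributed to 50 mg every 2 months. The SAP uses two incompatible descriptions for participants on an unchanged dose, and its ABR and safety sections omit the dose-level presentation that Protocol 10.2 and 10.2.6 require, with no recorded reason.

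The one size that follows from the documents is the contrast in nominal monthly dose, 2.0-fold to 3.2-fold (1.87 to 2.99 using the SAP's visit intervals). The effect on ABR, AEs or thrombosis is unknown and could be nil. The change should be made, but nothing here makes the pooled analysis invalid.

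**What to change.** - Define revised dose and regimen once, as either the whole post-pause scheme or the changed dosing, and reconcile SAP 4 with SAP 5.10.
- Report the number restarting on each regimen: 50 mg every 2 months, unchanged 50 mg monthly, unchanged 80 mg monthly.
- Keep the pooled column, and state in its title or footnote that it covers all participants after the 2020 pause, including those on an unchanged monthly dose.
- Add descriptive Set 2 summaries of ABR, AEs, AESIs and AT below 15% by restart regimen and final dose or frequency. Both are needed: a final 50 mg monthly dose can be unchanged or reached by escalation, and a final 50 mg every 2 months can follow a monthly restart that was later reduced.
- If the protocol's dose-level presentation is not to apply to Set 2, say so in SAP 2.7 with a reason.

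The cost is extra table columns. The SAP already uses treatment sequence for PD, and SAP 5.10 already separates reduced from unchanged dosing for visit assignment. The downside is small, non-randomised cells, more so when crossed with hemophilia and inhibitor type, so the split should stay descriptive and without formal comparison.
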